3.2.3 Mapping of assessments performed at Early Withdrawal Visit

Early Withdrawal assessments will be assigned to the next scheduled site visit (following the last scheduled visit that the participant completed prior to EW) where each assessment is evaluated as per protocol. This approach means that there is a chance that EW data will be mapped to different visits according to the schedule of assessments.

3.2.4 Dosing Regimen

Because no participants in TP0003 were randomized or treated under Protocol Amendment 3.0, analysis by dosing regimen will not be performed.

3.3 Definition of Baseline values

Baseline will be the last available pre-dose value prior to the first infusion of study drug in the Treatment Period, or if missing, the Screening value. Scheduled or unscheduled measurements can be used as the Baseline value. If an unscheduled measurement occurs after the planned baseline measurement time point but before dosing, then the unscheduled measurement will be used.

3.4 Protocol deviations

Important protocol deviations are deviations from the protocol which potentially could have a meaningful impact on study conduct or on the primary efficacy, key safety, or PK/PD outcomes (if applicable) for an individual participant. The criteria for identifying important protocol deviations will be defined within the appropriate protocol-specific document. Important protocol deviations will be reviewed as part of the ongoing data cleaning process and data evaluation. All important protocol deviations will be identified and documented prior to unblinding to confirm exclusion from the Pharmacokinetic Per-Protocol Set analysis set.

3.5 Analysis sets

3.5.1 Enrolled Set (ES)

All study participants who have signed the informed consent.

3.5.2 Randomized Set (RS)

The RS will include all enrolled study participants who were randomized. This is equivalent to the Intent-to-Treat Set.

3.5.3 Safety Set (SS)

The SS will include all randomized study participants who received at least one dose of IMP (partial or full). Analysis of this set will be according to the treatment the participants received and will be used for the demographic and safety analyses.

3.5.4 Full Analysis Set (FAS)

The FAS consists of all randomized study participants who have received at least one sufficient sc infusion of IMP, have a valid Baseline, and at least 1 valid post-Baseline platelet count measurement during Weeks 13-25.

Note: Due to the early termination of the study and changes to the analysis, the Full Analysis Set will not be included in the analysis and the clinical study report.

3.5.5 Pharmacodynamic Per-Protocol Set (PD-PPS)

The PD-PPS is a subset of the SS, consisting of those study participants who had no important protocol deviations potentially affecting the serum concentration of total IgG, as confirmed during a pre-analysis review of the data prior to database lock. Protocol deviations may not necessarily lead to total exclusion of a participant from the PD-PPS but may lead to exclusion of specific data.

Note: Due to the early termination of the study and changes to the analysis, the PD-PPS will not be included in the analysis and the clinical study report.

3.5.6 Pharmacokinetic Per-Protocol Set (PK-PPS)

The PK-PPS is a subset of the SS, consisting of those study participants who received at least 1 dose (as described above), had at least 1 valid PK measurement and no important protocol deviations affecting the PK variable, as confirmed during a pre-analysis review of the data prior to database lock.

3.6 Treatment assignment and treatment groups

If after unblinding it is determined that participants at any time received incorrect treatment from their randomized assignment, then for safety analyses these participants will be reallocated to the appropriate treatment group. For example, if participants randomized to placebo received rozanolixizumab, then for the safety analyses, these participants will be reallocated to rozanolixizumab.

Participants randomized to rozanolixizumab will only be reallocated to the placebo treatment group if they never received rozanolixizumab.

Efficacy data will be summarized by randomized treatment group as shown below:

- Placebo
- RLZ

Safety data will also be summarized based on the two groups and dose will not be shown in the header. Dose will be captured in the listings.

3.7 Center pooling strategy

It is planned to recruit participants in North America, Europe, and Asia in this study, with possible extension to other regions and countries. The data from all sites will be pooled for analysis purposes.

3.8 Coding dictionaries

Adverse events (AEs) will be coded using version 24.0 or later of the Medical Dictionary for Regulatory Activities (MedDRA®).

Medications will be coded according to version Mar 2021 or later of the World Health Organization Drug Dictionary (WHODD). Medical procedures will not be coded.

3.9 Changes to protocol-defined analyses

(1) Analysis sets

- (1.2) The FAS was removed from analysis
- (1.3) The PD-PPS was removed from analysis

(2) Added COVID-19 as an intercurrent event to all endpoints

(3) Note: The study was terminated early after 33 participants were randomized to bi-weekly infusions per Protocol Amendment 2; no participants were randomized to weekly infusions in the study per Protocol Amendment 3.

(4) No formal statistical analyses of efficacy endpoints were conducted. Only the primary and secondary efficacy endpoints were summarized descriptively and listed. Protocol-defined analyses for efficacy endpoints are described below.

The primary efficacy analysis of the study was planned to conduct a Stratified Cochran-Mantel-Haenszel test statistic. Sensitivity, supplemental and subgroup analyzes were planned to test the robustness of the assumption. The secondary efficacy analyses were planned to conduct a sequential hierarchical test procedure to protect the overall significance level for the multiplicity of endpoints.

Primary and secondary efficacy endpoints listed below will be listed and summarized descriptively for study participants randomized to bi-weekly dosing according to previous protocol versions.

- Durable Clinically Meaningful Platelet Response of $\geq 50 \times 10^9/L$ for at least 8 out of 12 weeks during the last 12 weeks (Week 13 to 25)
- Cumulative number of weeks with Clinically Meaningful Platelet Response of $\geq 50 \times 10^9/L$ over the 24-week treatment period (Week 1 to Week 25)
- Time to first Clinically Meaningful Platelet Response of $\geq 50 \times 10^9/L$: time from starting treatment to achievement of first response of $\geq 50 \times 10^9/L$
- Clinically Meaningful Platelet Response of $\geq 50 \times 10^9/L$ by Day 8

-
- Response defined as platelet count $\geq 30 \times 10^9/L$ and at least a 2-fold increase of the Baseline count confirmed on at least 2 separate occasions at two adjacent nominal visits at least 7 days apart, and absence of bleeding by visit
 - Time to first rescue therapy
 - Change from Baseline to Week 25 in ITP Patient Assessment Questionnaire (ITP-PAQ) Symptoms Score

Other efficacy endpoints listed below will be listed and summarized descriptively as well.

- Cumulative number of weeks over the planned 24-Week treatment period with platelet counts $\geq 30 \times 10^9/L$ and at least doubling from Baseline
- Mean change from Baseline in platelet count by visit

The data collected for all other efficacy endpoints will be listed only.

- (5) All sensitivity and supplemental analysis to the primary endpoint and to the secondary efficacy endpoints will not be performed
- (6) Subgroup analyses to the primary efficacy analysis will not be performed
- (7) Analysis for the PMDA on the Japanese subset of participants will not be performed
- (8) Change from baseline will not be calculated for the following endpoints. Only item responses will be listed.
 - Change from Baseline in European Quality of Life-5 Dimension 5 Levels (EQ-5D-5L) item responses
 - Change from Baseline in Short form 36-item (SF-36) domain and composite scores
 - Change from Baseline in the ITP-PAQ VI domain Scores
 - Change from Baseline in FATIGUE-PRO Physical Fatigue Score by visit
 - Change from Baseline in Patient Global Impression of Severity (PGI-S)
- (9) Percent change from Baseline will not be calculated for the following endpoint. Titers will be listed.
 - Percent change from Baseline in vaccination titers against *Streptococcus pneumoniae*, *Neisseria meningitidis*, and *Haemophilus influenzae* in splenectomized study participants
- (10) The following endpoint will not be analyzed because no samples were collected:
 - Change in biomarkers of COVID-19 vaccine response over time
- (11) Change from Baseline will not be calculated for the following safety endpoints. Only raw data will be listed.
 - Vital signs change from Baseline (blood pressure [BP], pulse rate, body temperature) at each scheduled assessment during Treatment and SFU Periods
 - 12-lead echocardiogram (ECG) change from Baseline at each scheduled ECG visit
 - Laboratory change from Baseline (hematology including coagulation parameters, clinical chemistry, and urinalysis) at each scheduled assessment during Treatment and SFU Periods

-
- Change from Baseline in concentrations of total protein and albumin
 - Change from Baseline in serum complement levels (C3 and C4) and plasma complement levels (C3a and C5a) at each scheduled assessment during the study (for study participants experiencing infusion reactions or hypersensitivity reactions)
 - Absolute values and change from Baseline (absolute values and percentage) in serum immunoglobulin concentrations (IgA, IgE, IgM) at each scheduled assessment

4 STATISTICAL/ANALYTICAL ISSUES

4.1 Adjustments for covariates/factors

No statistical analysis will be performed adjusting for covariates/factors.

4.2 Handling of dropouts or missing data

4.2.1 Handling missing data for the primary and secondary efficacy endpoints

Study participants who have not met the threshold for clinically meaningful response will be imputed as non-responders for the analysis. Missing platelet data at any visit will be considered "worst case" and set to zero ("no response") for that specific visit.

Missing data for ITP Patient Assessment Questionnaire (ITP PAQ) instrument will not be imputed.

Missing efficacy data encountered due to permanent treatment discontinuation due to TEAEs, or the receipt of rescue therapy will be considered as intercurrent events. For the primary efficacy analysis, patients with intercurrent events will be considered as non-responders.

Missing data strategy for PRO related endpoints will follow instructions indicated in each instrument.

4.2.2 Missing Data due to COVID-19

Unless specified otherwise, study participants who have visits impacted by COVID-19 for any reason will be considered non-responders at the corresponding visit, and missing platelet count data due to COVID-19 will be considered worst case and set to zero ("no response") for that particular visit.

4.2.3 Dates and times

Partially and completely missing dates may be imputed for the following reasons:

- Classification of Adverse events (AEs) as treatment-emergent
- Classification of medications as past, prior, or concomitant
- Durations of AEs.

Imputed dates will not be shown in listings. All dates will be displayed as reported in the database.

The following rules will be applied for partial start dates:

- If only start month and year are specified and are not the same as month and year of first dosing, then use the 1st of the month
- If only the month and year are specified and the month and year of first dosing is the same as the month and year of the start date, then use the date of first dosing. If this results in an imputed start date that is after the specified end date, then use the 1st of the start month, or the date of screening if this is later (if the latter imputation results in an end date that is earlier than the start date, then use the 1st of the month).
- If only the year is specified, and the year of dosing is not the same as the year of the start date then use January 01 of the year of the start date.
- If only the year is specified, and the year of dosing is the same as the year of the start date, then use the date of first dosing. If this results in an imputed start date that is after the specified end date, then use January 01 of the year of the start date, or the date of screening if this is later (if the latter imputation results in an end date that is earlier than the start date, then use January 01).
- If the start date is completely unknown, then use the date of first dosing. If this results in an imputed start date that is after the specified end date, then use January 01 of the year of the end date, or the date of screening if this is later (if the latter imputation results in an end date that is earlier than the start date, then use January 01).

Any medication with a start date on the first dosing date, will be assumed to be concomitant.

The following rules will be applied for **partial stop dates**:

- If only the month and year are specified, then use the last day of the month
- If only the year is specified, then use December 31 of the known year

If the stop date is completely unknown, do not impute the stop date, except for ITP medications where end date is missing and ongoing is ticked as “no”, which will be imputed as “Past” medications.

Imputed AE dates will be used for the calculation of duration of AEs as described in [Table 4-1](#).

Table 4-1: Calculation rules for duration of AEs

Data availability	Onset date	Outcome date	Calculation rules
Complete data	Analysis Start Date (D1)	Analysis End Date (D2)	Duration = D2 – D1 + 1 day
Start date partially or completely missing	--	D2	Duration = < D2 – D0 + 1 day Notes: D0 = imputed dose start date per partial stop dates .

Data availability	Onset date	Outcome date	Calculation rules
End date partially or completely missing	D1	--	
If end date is completely missing, then:
 
For ongoing AE Duration \geq (Discharge day – D1) + 1 day or Duration \geq (Data cut-off day – D1) + 1 day
 
For resolved AE: Duration \leq (Discharge day – D1) + 1 day or Duration \leq (Data cut-off day – D1) + 1 day
 
Note: Where discharge refers to the date when the participant rolls over TP0004, or the date of EOS visit for study completers, or date of discontinuation for participants that were withdrawn from the study.
 
If end date is partially missing, then: Duration = D3 – D1 + 1 day, where D3 is imputed end date using partial stop dates (see above).
 
For any AEs with known start date, if the end date is missing, the date of last contact will be used as the discharge day.
 
For participants still ongoing in the study at the time of the data cut-off, and for whom no discharge date is available, the date of the data cut-off will be used instead of the discharge date.

This document cannot be used to support any marketing authorization application and any extensions or variations thereof.

Data availability	Onset date	Outcome date	Calculation rules
Start and end date partially or completely missing	--	--	
For ongoing AE: Duration \geq (Discharge day – D0) + 1 day or Duration \geq (Data cut-off day – D0) + 1 day
 
For resolved AE: Duration \leq (Discharge day – D0) + 1 day or Duration \leq (Data cut-off day – D0) + 1 day
 
For a participant in the SS, D0 is the date of first administration of IMP, and for screen failures, D0 is the date of the screening visit.
 
Note: Discharge refers to the date of the end of study visit or the date of discontinuation from the study for participants that withdraw.
 
For any AEs with known start date if the end date is missing, the date of last contact will be used as the discharge day.
 
For participants still ongoing in the study at the time of the data cut-off, and for whom no discharge date is available, the date of the data cut-off will be used instead of the discharge date.

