6.5 Concomitant medications

Definitions:

Past Medications: defined as any medications that started and stopped before first administration of IMP.

This includes medications reported in the following eCRF pages:

- “ITP Treatment history”
- “Prior and Concomitant Medications”, if end date before first IMP date

-
- “Prior and Concomitant Medications ITP Treatment”, if end date before first IMP date.

Prior Medications: defined as any medications that started before the first administration of IMP.

This includes medications reported in the following eCRF pages:

- “ITP Treatment History”,
- “Prior and Concomitant Medications”, if start date before first IMP date.
- “Prior and Concomitant Medications ITP Treatment”, if start date before first IMP date.

Baseline Medications: defined as any medications that started prior to first administration of IMP and stopped after the first administration of IMP (classified as prior and concomitant medications). This includes medications reported in the following eCRF pages:

- “Prior and Concomitant Medications”, if start date before first IMP date and end date after first IMP date or ongoing
- “Prior and Concomitant Medications ITP Treatment”, if start date before first IMP date and end date after first IMP date or ongoing

Concomitant medications: defined as any medication that has been taken at least once after the first administration of IMP.

This includes medications reported in the following eCRF pages:

- “Prior and Concomitant Medications”, if end date after first IMP date or ongoing
- “Prior and Concomitant Medications ITP Treatment”, if end date after first IMP date or ongoing

Concomitant only medication: defined as any medication that started after first administration of IMP

This includes any medication reported in the following eCRF pages:

- “Prior and Concomitant Medications”, if start date after first IMP date
- “Prior and Concomitant Medications ITP Treatment”, if start date after first IMP date

Table 6-1 below summarizes concomitant medication classification with details around medication start and finish.

Table 6-1: Concomitant Medications Classification

Medication Started	Medication finished	Classification
Before 1st Dose IMP	Before 1st Dose IMP	Past Medications
Before 1st Dose IMP	Any time	Prior Medications
Before 1st Dose IMP	After 1st Dose IMP	Baseline Medications (= prior and concomitant)
Any time	After 1st Dose IMP	Concomitant

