After 1st Dose IMP	After 1st Dose IMP	Concomitant Only Medications

All the categories mentioned above will be summarized separately for ITP medications; Non-ITP medications will be listed only (using the RS) to display the number and percentage of participants in each category by treatment group, overall and by Anatomical Therapeutic Chemical classification (ATC) class, presenting Anatomical Main Group (ATC Level 1), Pharmacological Subgroup (ATC level 3), and preferred term.

Any medications with missing dates will be handled as described in Section 4.2.2 in order to classify them as prior and/or concomitant.

Listings for ITP medications will be also produced using the RS.

Notes:

- WHODD Mar2021 will be used for ATC terms.

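### SAP 4.2.3 classes every ITP medication with a missing end date and ongoing 'no' as Past, even when its recorded start is after the first dose of IMP

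*SAP*

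**What the plan says.** SAP 4.2.3 (Dates and times) sets the date rules used, among other things, to sort medications into past, prior and concomitant. Its default for a wholly missing stop date is to leave it unimputed. It then carves out one group of records, with the words "except for ITP medications where end date is missing and ongoing is ticked as", the answer in question being no. The outcome set for that group is "which will be imputed as “Past” medications". Neither the start date nor the eCRF page is mentioned. The same section assumes that a medication starting on the first dosing date is concomitant, and it imputes a completely unknown start to the first dosing date.

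SAP 6.5 (Concomitant medications) defines the classes:

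- Past: "defined as any medications that started and stopped before first administration of IMP".
- Concomitant only: "defined as any medication that started after first administration of IMP".
- Concomitant: taken at least once after first dose. For the two eCRF pages on prior and concomitant medications this is applied as "if end date after first IMP date or ongoing".

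On output, "All the categories mentioned above will be summarized separately for ITP medications", while non-ITP medications are only listed. On missing dates, "Any medications with missing dates will be handled as described in Section 4.2.2 in order to classify them as prior and/or concomitant". SAP 4.2.2 concerns data missing because of COVID-19; the date rules are in 4.2.3.

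**The concern.** A drug that started after the first dose cannot have stopped before it. Read as written, the 4.2.3 exception still puts such a drug in the Past class if its end date is missing and ongoing is answered no. ITP medications are the only medications tabulated by class, so the error would appear in a summary table. ITP treatment actually given on study would be missing from the concomitant ITP tables and would be shown as treatment that ended before the trial. With only descriptive efficacy output planned (SAP 3.9), those tables are part of how a reader would judge what else could have influenced platelet counts.

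**Working it through.** The plan states no figure on this point, so the check is to apply the rules of SAP 4.2.3 and 6.5 to one kind of record: an ITP medication, end date completely missing, ongoing answered no. The result depends on the start date.

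1. **Start before first dose.** The 4.2.3 exception gives Past. The drug may have stopped before or after first dose; the record does not say. Past is a convention here, and it does not contradict the recorded start.
2. **Start on the first dosing date.** The exception gives Past. The 4.2.3 sentence on starts on that date gives concomitant. The section contradicts itself.
3. **Recorded start after first dose.** The exception gives Past. The 6.5 definition gives Concomitant only, which needs nothing beyond the start date. Whatever the true stop date was, it cannot precede the start, so it also falls after first dose. The Past definition cannot be met.
4. **Start completely unknown.** With no end date to override it, 4.2.3 imputes the start to the first dosing date. The record then falls into the same contradiction as case 2.

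Partial end dates are not affected, because 4.2.3 imputes them to the end of the month or year.

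Next, does 6.5 recover case 3? Its page rule for Concomitant requires an end date after first dose or an ongoing record, and this record has neither. Its Concomitant-only rule would keep the record. However, 6.5 hands missing dates to the missing-date rules (with the wrong section number), and the SAP does not say which section prevails. Taken literally, 4.2.3 decides, and the record moves from the Concomitant and Concomitant-only tables to the Past table.

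Which outputs depend on the class?

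- Rescue therapy table (SAP 6.6.2): built from a CRF tick, not from the class.
- Time to first rescue (SAP 8.2.5): date of first rescue use minus date of first treatment plus 1, so no stop date is needed.
- Primary-endpoint intercurrent event (SAP Table 8-1): use of rescue therapy, with no reference to the class.
- Listings: ITP medications are listed, and 4.2.3 displays dates as reported.

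Size per affected participant, from the 33 randomized (SAP 2.3 and 2.4) and the planned 2:1 ratio. The actual arm sizes are not given, so an exact split is assumed:

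- Rozanolixizumab: 33 × 2/3 = 22; 1/22 = 4.5 points.
- Placebo: 33 × 1/3 = 11; 1/11 = 9.1 points.
- Overall column: 1/33 = 3.0 points, which does not depend on the split.

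A participant who also has a correctly classed record in the same table row would not move that row.

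**The case against.** The best defence is that a sensible reading already exists. Concomitant only depends on the start date alone, so a recorded post-dose start settles the class without a stop date, and a programmer who gave 6.5 precedence would lose nothing from that table. This stands as far as it goes: the fault is a conflict between two sections, and loss of the record is the result of one of two readings. It does not remove the point, because no precedence is stated, 6.5 itself defers to the date rules, and the page rule for the broader Concomitant class would still miss the record.

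A reader might infer that rescue exposure, and through it the primary endpoint, is also wrong, because Protocol 6.4.3 counts additional ITP treatment as rescue. The documents do not support that. Rescue is identified by its own CRF tick and timed by its start, so a correctly ticked course stays in the rescue output whatever its class.

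A reader might also infer that the baseline counts of prior ITP medications are inflated, or that background treatment is misstated. Prior is defined in 6.5 by a start before first dose, which a drug started on study does not meet. Background drugs also start before first dose, so they are not the case at issue.

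Finally, nothing in the documents shows that on-study courses lack stop dates. Protocol 6.4.3 requires the date, time and dosage regimen of rescue therapy in the eCRF. The pattern may be rare or absent.

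**Conclusion.** The rule is wrong as written. For an ITP medication with a recorded start after first dose, a completely missing end date and ongoing answered no, SAP 4.2.3 assigns a class that SAP 6.5 makes impossible. For a start on, or imputed to, the first dosing date, 4.2.3 contradicts itself. The harm is confined to the ITP medication tables: the record can be lost from Concomitant and Concomitant only and added to Past. The same drug could then appear as rescue therapy in one table and as Past in another. Rescue and efficacy results are not affected.

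The number of records is unknown and may be zero. The 4.5-point and 9.1-point figures are per affected participant and rest on the assumed 22/11 split. This is a small point, but easily settled before the tables are programmed.

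**What to change.** In SAP 4.2.3, limit the Past exception to ITP medications that are recorded on the ITP Treatment History page, or that have a recorded or partially imputed start before first dose. State that ITP medications with a start on or after first dose are Concomitant whatever the stop date. Say explicitly that this includes a completely missing start that is imputed to the first dosing date, when the record is on the eCRF page for prior and concomitant ITP treatment. Without that sentence, such a record would still fit both classes. Extend the 6.5 page rule for Concomitant to match, and correct its cross-reference from 4.2.2 to 4.2.3.

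The cost is a short edit to two sections and the matching derivation code. No new data are needed. Case 1, a pre-dose start with an unknown stop, remains Past by convention; a footnote to the tables could say so.
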